9 INTERIM ANALYSIS

No interim analysis is planned in this trial.

10 GENERAL DEFINITIONS AND DERIVATIONS

This section describes all recurrent general definitions (e.g., study treatment start date, baseline, study day) which will be used for the derivations of variables and summary tables and are not covered in the sections above.

10.1 Handling of screening and re-screening data

Data of re-screened subjects obtained at the re-screening visit will be used as 'Screening' data. If a data point is not collected at re-screening but was collected at the previous screening visit, the data point from the screening visit will be used.

10.2 Analysis periods and visit windows

10.2.1 Study treatment start and end date

The date and time of the first infusion of i.v. selexipag will be considered study treatment start date/time. The end date and time of the last infusion of i.v. selexipag will be considered study treatment end date/time.

10.2.2 Study days

The day of intake of the Uptravi during pre-treatment period, i.e., Period 1 [see Section 2.3] will be considered Day 1. There is no Day 0; the day before Day 1 will be considered Day -1.

Note that study treatment will be administered on Day 2 and Day 3 according to this definition; thus study day definition corresponds to the study days used in the study protocol.

10.2.3 Baseline

All assessments on Day 1 will be considered baseline. If a Day 1 assessment is not available, the last assessment prior to Day 1 will be considered baseline.

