6. If Visit 1 and Visit 2 Day 1 are performed within 7 days, laboratory tests do not have to be repeated at Visit 2 Day 1.
7. ECG will be performed at pre-dose and within 30 minutes after stopping of infusion (i.v. selexipag).
8. PK profile includes 7 blood samples. Timing of blood samples is detailed in [Table 3](#)
9. Infusion solution samples will be taken from the tubing before each infusion [see [Table 3](#)].
10. All AEs and SAEs that occur after signing the Informed Consent Form and up to 30 days after i.v. selexipag study treatment discontinuation must be reported.

Table 3 Visit 2 vital signs and PK blood collection schedule

	Visit 2 (hospitalization)														Period 3 (Uptravi, Post-treatment Period)								
	Period 1 (Uptravi, Pre-treatment Period)							Period 2 (Treatment Period; i.v. selexipag)															
	Day 1							Day 2							Day 3								
Time ¹ after morning dose	0 h	1 h	2 h	4 h	6 h	8 h	12 h	0 h	25 min	87 min	4 h	6 h	8 h	12 h	0 h	25 min	87 min	4 h	6 h	8 h	12 h		
Uptravi oral intake	X						X															X	
Infusion solution sample ²								X							X	X							
Selexipag i.v. infusion								X	—————>						X ⁵	X	—————>						
PK blood sample	X ³	X	X	X	X	X	X ³								X ³	X	X ⁴	X	X	X	X ³		
Vital signs (pulse rate and BP)	X							X ³	X	X ⁴	X	X	X	X ³	X ³	X	X ⁴	X	X	X	X ³		

BP = blood pressure; i.v. = intravenous; PK = pharmacokinetic.

¹ A time window of \pm 5% is allowed for PK time points.

² Infusion solution sample will be taken from the tubing prior to selexipag infusion.

³ Vital signs and PK blood sample must be assessed/taken before selexipag administration (oral or i.v.).

⁴ Immediately before stopping the infusion.

⁵ Evening i.v. selexipag infusion to be started 12 h \pm 1 h after the start of the morning infusion.

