10.2.3.3 ECG

ECG analyses are based on data received from the central ECG. All transferred central ECG data are taken into account regardless of whether they correspond to scheduled or unscheduled assessments.

Baseline ECG refers to the latest ECG performed prior to the start of study treatment.

All ECG values collected will be listed. Descriptive summary statistics of each variable (HR and the intervals PR, QRS, QT, QTcF and QTcB) by visit will be provided for observed values and absolute changes from baseline.

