5.5 Study treatment exposure and compliance

i.v. selexipag is considered the only study treatment for this study.

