7.6.1 Variables

The 12-lead ECG encompasses 3 categories of data obtained via the central ECG laboratory:

- Measurements:
 - ECG mean heart rate
 - PR interval,
 - QRS duration,
 - QT interval,
 - QTcB interval,
 - QTcF interval,
- Interpretation (normal/abnormal/unable to evaluate)
- Qualitative findings by category, as specified in the ECG data transfer specifications:

Table 11 Pre-specified ECG findings categories

Category
Atrioventricular Conduction
Axis and Voltage
Chamber Hypertrophy or Enlargement
Intraventricular-Intraatrial Conduction
Myocardial Infarction
Pacemaker
Sinus Node Rhythms and Arrhythmias
Supraventricular Arrhythmias
Supraventricular Tachyarrhythmias
ST Segment, T Wave and U wave
Ventricular Arrhythmias
Ventricular Tachyarrhythmias

ECG assessments will be performed at Visit 2 Day 1, Visit 2 Day 2 (pre-dose and 30 min after end of infusion for each of the two infusions), Visit 2 Day 3 (pre-dose and 30 min after end of infusion), Visit 3, and at unscheduled visits.

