7.6.2 Variables

The following variables will be defined for the analysis of ECG parameters:

- Baseline values of quantitative ECG parameters
- Value at each post-baseline visit
- Absolute change from baseline to each post-baseline visit
- Absolute change from pre-dose after each infusion
- Proportion of qualitative ECG abnormalities

In addition, the incidence of QT prolongations is derived according to the criteria defined in [Table 12](#) below:

Table 12 QT prolongations in ECG parameters

Analysis Parameter	Analysis Variable(s)	Analysis Criterion
QTcB (msec)	Analysis value	- Value > 450
QTcF (msec)		- Value > 480 - Value > 500
	Change from baseline	- Increase from baseline > 30 - Increase from baseline > 60
	Analysis value and change from baseline	- Value > 450 and increase from baseline > 30 - Value > 450 and increase from baseline > 60

ECG = electrocardiograph; QTcB = QT interval corrected using Bazett's formula;
QTcF = QT interval corrected using Fridericia's formula.

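### The SAP uses Day 1 as the ECG baseline where the protocol uses the last ECG before the first infusion; the change is undeclared and can alter which subjects meet the QTc criteria

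*SAP*

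**What the plan says.** Protocol 10.2.3.3 defines baseline for ECG specifically: "Baseline ECG refers to the latest ECG performed prior to the start of study treatment". Two SAP statements fix when that is. SAP 5.5 says "i.v. selexipag is considered the only study treatment for this study", and SAP 10.2.1 says "The date and time of the first infusion of i.v. selexipag will be considered study treatment start date/time". The first infusion is given on the morning of Day 2.

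Both documents schedule an ECG on Day 1 and a separate one before that infusion. Protocol Table 2, footnote 7, reads "ECG will be performed at pre-dose and within 30 minutes after stopping of infusion (i.v. selexipag". SAP 7.6.1 lists Day 1 and then "Visit 2 Day 2 (pre-dose and 30 min after end of infusion for each of the two infusions".

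SAP 10.2.3 applies one rule to all data: "All assessments on Day 1 will be considered baseline". Its fallback looks only backwards: "If a Day 1 assessment is not available, the last assessment prior to Day 1 will be considered baseline". There is no ECG exception. The footnotes of shells T_EG_SUM and T_EG_QUAL repeat the Day 1 definition, and both shells show the IV-1 pre-dose ECG as a row after baseline.

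SAP Table 12 (section 7.6.2) counts QTcB and QTcF by criteria such as "Increase from baseline > 30". SAP 11.1 declares no changes to the protocol analyses. Neither SAP 11.3 nor the document history in Appendix F mentions the ECG baseline.

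**The concern.** ECG abnormalities are a listed safety endpoint in protocol 6.2.3, to be analyzed by period. The baseline enters every QTc category:

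- The increases above 30 and 60 ms use it directly, alone and combined with a value above 450 ms.
- The absolute thresholds of 450, 480 and 500 ms use it through the T_EG_ABN footnote, which counts a value only if it is new or worsened relative to baseline.
- T_EG_QUAL leaves out post-baseline findings that were already present at baseline.

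The i.v.-period counts would therefore be taken against a different ECG from the one the protocol names, while the SAP tells the reader that nothing has changed. With about 18 subjects, one or two flagged subjects are the result, so it matters who is flagged. The Day 1 ECG also has no stated timing relative to the oral dose, whereas the IV-1 pre-dose ECG is fixed as pre-infusion.

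**Working it through.** There is no stated figure to reproduce. The check has two parts: whether the two rules select different ECGs, and how much that could matter.

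**Which ECG each rule selects**

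- Protocol: latest ECG before study treatment. Study treatment is i.v. selexipag and starts with infusion 1 on Day 2. The last scheduled ECG before it is IV-1 pre-dose on Day 2.
- SAP: the Day 1 ECG or, if that is missing, an earlier one. Protocol Table 2 and SAP 7.6.1 schedule no ECG before Day 1, so a subject without a Day 1 ECG would usually have no SAP baseline even when the IV-1 pre-dose ECG exists.
- The two rules coincide only if the IV-1 pre-dose ECG is missing and no unscheduled ECG falls between Day 1 and the first infusion.

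**How a subject can change status (assumed values, ms)**

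- Day 1 = 430, IV-1 pre = 445, post-infusion = 465. SAP: 465 − 430 = 35, counted. Protocol: 465 − 445 = 20, not counted.
- Day 1 = 445, IV-1 pre = 425, post-infusion = 460. SAP: 460 − 445 = 15, not counted. Protocol: 460 − 425 = 35, counted.

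**Size under stated assumptions**

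The documents give no QTc mean, SD or shift, so all of these are assumptions: subject mean 420 ms with between-subject SD 20 ms, independent normal within-subject error with SD s, no drug effect, and five Period 2 ECGs (IV-1 post, IV-2 pre and post, IV-3 pre and post). Let M be the highest of the five, B1 the Day 1 value and B2 the IV-1 pre-dose value. The share reclassified is

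D = P[(M − B1 > 30) differs from (M − B2 > 30)].

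The subject's own mean cancels from these differences, so D depends only on s. Simulation of 200,000 subjects gave:

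| s (ms) | Counted, Day 1 | Counted, IV-1 pre | D | 18 × D | 1 − (1 − D)^18 |
|---|---|---|---|---|---|
| 8 | 1.73% | 1.74% | 3.11% | 0.56 | 0.43 |
| 12 | 13.38% | 13.34% | 19.26% | 3.47 | 0.98 |
| 15 | 24.08% | 24.08% | 29.72% | 5.35 | 0.998 |

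The last column is the chance that at least one of 18 subjects changes status. For a new or worsened value above 450 ms, status differs in 2.8% (s = 8) to 3.8% (s = 12) of subjects with a mean of 420 ms, and in 7.9% to 9.2% with a mean of 435 ms.

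Columns two and three agree because the two baselines are exchangeable in this model: subjects move in both directions and the expected total hardly changes.

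**The case against.** The strongest reply is that Day 1 has a good reason behind it. Protocol 6.2.3 requires ECG abnormalities for Period 1 alone and for Periods 1 and 2 combined. Period 1 ends just before the first infusion, so the only scheduled ECG after Day 1 in that window is IV-1 pre-dose. If that ECG is the baseline, Period 1 has no scheduled post-baseline ECG. Protocol 5.1.5 and Table 2 also label Visit 2 Day 1 as baseline. This stands as a reason to keep Day 1 for columns that include Period 1. It does not override an ECG-specific definition without declaration, and it gives no reason to use Day 1 for the i.v.-period columns.

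The second reply is that the information is largely there already. Shell T_EG_PREDS gives mean, SD, median, minimum and maximum of the change from pre-dose, including QTcB and QTcF, and L_EG lists every value. For infusion 1 the pre-dose value is the protocol baseline, so the maximum shows whether any scheduled reading after that infusion rose by more than 30 or 60 ms. A reader might infer that only means are available against pre-dose; the shell shows otherwise. What is missing is any categorical count on that baseline. For infusions 2 and 3, moreover, the pre-dose value follows i.v. exposure.

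Third, the endpoint is listed among the other, not the main, safety endpoints. The study is descriptive and has no QTc decision rule. That limits the weight of the point but does not make the statement in SAP 11.1 correct.

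**Conclusion.** The SAP departs from the protocol's ECG baseline, the departure runs through the shells, and SAP 11.1 is wrong to declare no changes. The consequence is possible reclassification of individual subjects: about 3% to 19% on the 30 ms criterion, or 0.6 to 3.5 of 18, if the within-subject SD is 8 to 12 ms, there are five Period 2 ECGs and there is no drug effect. These figures are illustrative.

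Two stronger readings are not supported. A reader might infer that Day 1 biases the QTc counts up or down. With exchangeable baselines the expected totals are about equal, and the documents contain nothing that shows a systematic difference between the Day 1 and IV-1 pre-dose ECGs. A reader might also assume a QTc shift of, say, 15 ms. Disagreement on a single reading is then 13% to 22% over the same SD range, but it is about 1% to 6% with no shift. The documents state no shift, the i.v. dose targets the same metabolite exposure as the oral dose (protocol 1.4), and the bioavailability study reported no clinically significant ECG abnormality (protocol 1.2.4). T_EG_ABN also counts subjects over several ECGs, so a single-reading rate cannot be turned directly into a number of subjects.

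**What to change.** Either of two changes resolves the conflict.

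1. In SAP 10.2.3, T_EG_SUM, T_EG_ABN and T_EG_QUAL, use the last ECG before the first infusion as baseline for Period 2, Period 3 with follow-up, and Periods 2 and 3 with follow-up. Keep Day 1 for Period 1 and for any combined column that includes Period 1, and declare that exception with its reason in SAP 11.1. The rule for combined columns is needed because SAP Table 7 plans ECG abnormalities for Periods 1 and 2 and for all periods together.
2. Keep Day 1 throughout, declare the change with its reason in SAP 11.1, and add a table of the SAP Table 12 QTc categories against the IV-1 pre-dose ECG.

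Both use ECGs already scheduled. The cost is one extra derivation or table, and two ECG baselines that must be labelled clearly wherever they appear.

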10.2.4 Unscheduled visits and visit windows

Assessments made on both, scheduled and unscheduled visits will be assigned to an analysis period according to [Table 2](#) using the assessment date and time.

Furthermore, each assessment will be assigned an analysis visit using the time windows described in [Table 13](#). If more than one assessment was made within a visit time window, the closest value to the target Visit is displayed in by visit displays.

Table 13 Analysis visit windows

Analysis visit	Nominal study day*	Lower bound study day*	Upper bound study day*
Visit 2, Day 1	Day 1	Day of informed consent	Day 1
Visit 2, Day 2	Day 2	Day 2	Day 2
Visit 2, Day 3	Day 3	Day 3	Day 3
Visit 3	Day 12	Day 4	Day 22
Visit 4	Day 33	Day 23	End of Study

* Study days are defined as in Section [10.2.2](#).

10.3 Utravi dosage subgroups

Enrollment is controlled by an interactive response technology system based on the subject's stable Utravi dose. For analysis purposes, the information entered into the system will determine the allocation to one of the two dosage subgroups.

10.4 Derived and computed variables for analysis datasets

CDISC ADaM version 2.1 and ADaM implementation guide 1.1 will be followed.

For details on the derivation of specific analysis variables, please refer to the programming specifications document.

10.5 Handling of missing/incomplete date and time fields

Missing parts for specific dates/times will be changed into acceptable non-missing values as described in the table below.

Type of date/time	Imputation method when date/time is incomplete	Imputation method when date/time is missing
Start Date/Time of Adverse Event	If the end date of the AE is not before the start of study treatment, and if the study treatment start falls in the range of possible dates, the study treatment start date is used. In all the other cases, the lower limit (i.e., first day of the month, 00:00h) is used.	Date & time of first i.v. selexipag
End Date/Time of Adverse Event	Use the upper limit of the range of possible dates given the nonmissing date/time parts, i.e., last day of the month or last day of the year, 23:59h	No approximation, the AE is considered ongoing at end of study

Start Date of Medication	If the date of the Screening visit is within the range of possible dates, use the Screening visit date. Otherwise, use first day of the month and/or first day of the year.	Date of Screening visit
End Date of Medication	Use the upper limit of the range of possible dates given the nonmissing date/time parts, i.e., last day of the month or last day of the year	No approximation, the medication is considered ongoing at the end of study
Date of initial diagnosis of PAH	Day missing: 15th of the month Day and month missing: 30th of June If the resulting date is later than the date of screening visit date and the lower limit is not later than the screening visit date, then the date is substituted with the date of screening visit.	No replacement
PK sample Date/Time	If the scheduled time is within the possible range given the nonmissing date/time parts, use the scheduled date/time. Otherwise, the sample date/time cannot be imputed.	No replacement

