10.2.3.1 Adverse events

An AE is defined as any event that is recorded on the AE CRF module regardless of the onset date. The onset date will determine which events belong to each of the treatment periods (i.e., before/after intake of oral/i.v. selexipag). All events during the study will be listed and/or tabulated accordingly. In the event of partially missing dates/times, imputation will be carried out to link event and period using a conservative algorithm.

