2.3 Analysis periods

The study comprises five analysis periods:

Screening period: This period starts with the signing of the Informed Consent Form and ends with the first day of Period 1 (Visit 2 Day 1).

Period 1 (Uptravi, pre-treatment period, in-hospital): This period starts with intake of the morning dose of Uptravi at Visit 2 Day 1, and ends the following day before initiation of the first infusion of i.v. selexipag.

Period 2 (i.v. selexipag, treatment period, in-hospital): This period starts in the morning of Visit 2 on Day 2 with the start of the first infusion of i.v. selexipag, and ends after approximately 36 hours in the evening of Visit 2 on Day 3 with the resuming of administration of Uptravi at the evening dose.

Period 3 (Uptravi, post-treatment period): This period starts in the evening of Visit 2 Day 3 with the first dose of resumed oral administration of Uptravi, and ends 7 to 11 days later at Visit 3.

Safety follow-up period: This period starts at the end of Visit 3 and ends 30 to 37 days after the last administration of i.v. selexipag with the End-of-Study (EOS) telephone call (Visit 4).

[figure not shown]
A summary of analysis periods is presented in [Table 2](#):

Table 2 Summary of analysis periods

Period	Start	Stop
Screening period	Date/time of first Informed consent form signature	Prior to morning dose of Uptravi at Visit 2 Day 1
Period 1: Uptravi, pre-treatment period	Date/Time of Uptravi morning dose intake at Visit 2 Day 1	Prior to start of first infusion of i.v. selexipag at Visit 2 Day 2
Period 2: i.v. selexipag, treatment period	Start date/time of first infusion of i.v. selexipag at Visit 2 Day 2	Prior to evening dose of Uptravi at Visit 2 Day 3
Period 3: Uptravi, post-treatment period	Date/time of Uptravi evening dose intake at Visit 2 Day 3	Visit 3
Safety follow-up period	After end of Visit 3	End of Study

The study design and flow is shown in Figure 1 below. For details, refer to section 3 and section 7 of the AC-065A309 study protocol [D-17.055].

Figure 1 Study design and flow

* 12-hour PK profile after the morning dose.

** For convenience, hospitalization may be extended to the night before Day 1 and to the night of Day 3.

D = day; EOS = End-of-Study; IV1–IV3 = dose of i.v. selexipag; PK = pharmacokinetic; V = visit.

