7.2.2 Analysis

The start date/time of the AE record from the CRF will be used to assign the AE to a study period.

Summary tables will be prepared as described in [Table 8](#) for the periods mentioned in [Table 7](#), except for the screening period.

Summary tables by SOC and PT will display the number and percentages of subjects with at least one AE in the respective primary SOC and at least one AE at the PT level. Summaries will be sorted by descending total frequency of SOCs and PTs and alphabetically in case of ties.

Summary tables by PT will display the number and percentages of subjects with at least one AE in the respective PT. Summaries will be sorted by descending total frequency of PTs and alphabetically in case of ties.

AEs occurring during the Screening period, i.e., prior to first dose of Uptravi on Visit 2 Day 1, will be listed.

Due to the small number of subjects, conservative 95% Clopper-Pearson CIs for the proportions will be computed using exact methods.

All AEs occurring during the study from date of informed consent signature to EOS will be listed.

For any injection site reaction (irrespective of clinical significance), the worst grade, criteria of the injection site reaction, as well as its clinical significance will be summarized. Any AEs associated with clinically significant injection site reactions will be summarized by PT and by maximum intensity in the AE table.

Table 8 Overview of adverse event analyses

Category	Approach
All AEs	
- N (%) of subjects having at least one AE by primary SOC and PT- N (%) of subjects having at least one AE by PT- N (%) of subjects having at least one AE by PT and maximum intensity- Listing
SAEs	
- N (%) of subjects having at least one SAE by PT- Listing
Injection site reaction AEs	
- N(%), grade and diagnosis criteria of injection site reactions- N (%) of subjects having at least one clinically significant injection site reaction by PT and maximum intensity- Listing of PTs and specific details
Prostacyclin-associated AEs	
- N (%) of subjects having at least one prostacyclin associated AE by PT- N % of subjects having at least one prostacyclin associated SAE by PT- N % of subjects having least one prostacyclin associated AE leading to discontinuation of study drug by PT- Listing

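### SAP 10.5 sends every Day 1 adverse event with no clock time to Screening, so it is listed but not counted in the AE tables that include Period 1

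*SAP*

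**What the plan says.** Protocol 10.2.3.1 lets the onset date decide which period an AE belongs to, naming both oral and i.v. intake as boundaries. For partly missing dates or times it says that "imputation will be carried out to link event and period using a conservative algorithm".

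SAP 10.5 gives the algorithm. If the AE did not end before study treatment began, and "if the study treatment start falls in the range of possible dates, the study treatment start date is used". For everything else: "In all the other cases, the lower limit (i.e., first day of the month, 00:00h) is used".

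Study treatment here means the i.v. drug only. SAP 10.2.1: "The date and time of the first infusion of i.v. selexipag will be considered study treatment start date/time". SAP 10.2.2: "Note that study treatment will be administered on Day 2 and Day 3 according to this definition".

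The period boundaries are in SAP 2.3, Table 2. Screening stops "Prior to morning dose of Uptravi at Visit 2 Day 1", and Period 1 starts at "Date/Time of Uptravi morning dose intake at Visit 2 Day 1".

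SAP 7.2.2 assigns AEs to periods by start date and time and leaves Screening out of the summary tables. What remains for those events is this: "AEs occurring during the Screening period, i.e., prior to first dose of Uptravi on Visit 2 Day 1, will be listed".

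**The concern.** Two boundaries matter for counting AEs: the Day 1 morning oral dose, which opens the tabulated part of the study, and the first infusion on Day 2. The imputation rule protects only the second. At the first boundary, the 00:00h default puts an untimed event on the side where it is not tabulated.

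Protocol 6.2.2 analyses the main safety endpoints over Periods 1, 2, 3 and follow-up combined, so an event lost at the Day 1 boundary is lost from the main combined count as well as from Period 1. Period 1 lasts about one day, so Day 1 makes up most of it.

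The rule is also uneven. An AE with no start date at all is set to the first infusion and counted, while an AE known to have begun on Day 1 is not counted.

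**Working it through.** The plan states no figure for this point, so there is none to reproduce. The check traces the rule and then sizes the effect.

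**Trace for an AE dated Day 1 with no time**

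1. Possible range: Day 1 00:00h to 23:59h.
2. Study treatment start: first infusion, Day 2 (SAP 10.2.1 and 10.2.2). This is outside the range, so the first-infusion branch cannot apply, whatever the AE end date.
3. Default branch: the lower limit, Day 1 00:00h. SAP 10.5 illustrates the lower limit only as the first day of a month. Read literally, that is no later than Day 1 00:00h and gives the same result.
4. Day 1 00:00h is before the morning Uptravi dose, so Table 2 places the event in Screening.
5. SAP 7.2.2: listed, not tabulated.

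Dose clock time is not given in the documents. With the morning dose assumed at 06:00, 08:00 or 10:00, and the AE ending before or after the first infusion, all 3 x 2 = 6 cases end in Screening.

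**Comparison with other incomplete starts** (lower limit taken as the known day at 00:00h where the day is known)

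| What is known of the start | AE end | Imputed start | Period assigned |
|---|---|---|---|
| Day 1, no time | any | Day 1 00:00h | Screening |
| Day 2, no time | not before first infusion | first infusion | 2 |
| Day 2, no time | before first infusion | Day 2 00:00h | 1 |
| Day 3, no time | after first infusion | Day 3 00:00h | 2 |
| Month containing Day 1 only | between Day 1 morning dose and first infusion | first of month 00:00h | before Period 1 |
| Nothing | not before first infusion | first infusion | 2 |

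An event known to have started on Day 2 or Day 3 always stays in a tabulated period. One known to have started on Day 1 never does.

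**How often the assignment could be right.** The share of Day 1 clock time that belongs to Period 1 is (24 - dose hour)/24. At 06:00 it is 18/24 = 75%; at 10:00 it is 14/24 = 58%. So 25% to 42% of the day is truly Screening under these assumed times. The rule assigns 100% to Screening.

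**Tables affected.** Those that can hold a Day 1 onset under SAP Table 7: Period 1, Periods 1 and 2, and Periods 1 to 3 with follow-up.

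**Size.** The tables count subjects with at least one event, so one affected subject changes a row by at most 1/N:

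- Safety Analysis Set, about 20 subjects (SAP 2.5): 1/20 = 5 points. With exact Clopper-Pearson 95% limits, a true 1/20 (0.1% to 24.9%) would be shown as 0/20 (0% to 16.8%).
- Group A, 5 to 8 subjects (SAP 2.1): 1/8 = 12.5 to 1/5 = 20 points.
- Group B, 12 to 15 subjects: 1/15 = 6.7 to 1/12 = 8.3 points.

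These are maxima. If the subject has another counted event in the same row and period, the row does not change.

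**The case against.** The best case for leaving the rule alone has four parts.

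- **Rarity.** Protocol 9.1.4 requires onset time for AEs, Day 1 is spent in hospital, and data queries run until database closure (Protocol 11.3). The number of untimed Day 1 events may be zero. This stands, and it keeps the point small.
- **The assignment may be right.** Subjects have already consented, may be in hospital from the night before, and have vital signs and a blood sample taken before the dose. A reader might infer that every untimed Day 1 event is misassigned. The documents do not support that; some may truly be pre-dose. What stands against the rule is that it resolves every doubtful case the same way, towards not counting.
- **The protocol does not define conservative.** I.v. selexipag is the only study treatment, and protecting its start could be called conservative for that drug. That covers the first-infusion branch. It does not cover the counts over Periods 1 to 3 and follow-up combined, where dropping an event is the less cautious choice.
- **Detail is left to programming specifications** (SAP 10.4). But SAP 10.5 states the rule outright, and a programmer who follows it gets this result.

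Two other passages might seem to rescue the event. SAP Table 7 ticks a Screening column for AEs and SAEs, and Protocol 10.3.4 plans a descriptive analysis of procedure-related AEs before the first Day 1 dose. SAP 7.2.2 and the output list in SAP 12 provide only listings for Screening, so the event still reaches no summary table.

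**Conclusion.** The gap is real and narrow. An AE known to have started on Day 1 without a clock time is always assigned to Screening and is not counted in the AE tables for Period 1, Periods 1 and 2, or Periods 1 to 3 with follow-up. That falls short of the conservative link of event to period that the protocol promises. The cost is at most 5 points of a Safety Analysis Set incidence per affected subject, within the group ranges worked out above. It rests on planned enrolment and on the subject having no other counted event in that row.

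Three stronger readings are not supported:

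- The event does not leave every AE display. Tables for Period 2, for Period 3 with follow-up, and for Periods 2 and 3 with follow-up would not hold a Day 1 onset anyway. The event stays in the listing of all AEs and in the Screening listing.
- Discontinuation due to prostacyclin-associated AEs, which drives the sample size, is untouched. SAP Table 7 plans that table and the injection-site table for Period 2 only.
- A material bias in an oral versus i.v. safety comparison cannot be claimed. Safety is descriptive, the documents name oral selexipag as the reference treatment only for pharmacokinetics, and the periods already differ in length (1 day, 36 hours, then 7 to 11 days plus follow-up).

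For month-only AEs that ended between the Day 1 morning dose and the first infusion, true onset may well lie in Screening. There the point is only that the default is not conservative.

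**What to change.** In SAP 10.5, keep the first-infusion rule as the first step for an incomplete AE start, and replace the default with:

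> If that rule does not apply, and the Day 1 morning Uptravi date/time lies in the range of possible start dates/times, and the AE did not end before that dose, use the Day 1 morning Uptravi date/time. In all other cases use the lower limit of the possible range (the known day at 00:00h if only the time is missing).

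The new step should depend on the first-infusion rule not applying, rather than on the infusion lying outside the range. A month-only AE that ended on Day 1 after the morning dose can have the infusion inside its range and still fail the end-date condition. Worded as above, that case is covered and no branch is left undefined. The last clause also settles the case where the day is known and only the time is missing, which the present text does not spell out.

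The cost is two sentences and a small programming change. No new data are needed, because the Day 1 morning Uptravi clock time is already recorded in the CRF (Protocol 5.2.3). The downside is that a few true pre-dose Day 1 AEs may be counted in Period 1. Flagging imputed start times in the AE listing would let a reader see which events these are.
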